Appendix C. Insulin Infusion

INSULIN INFUSION TO OBTAIN EUGLYCEMIA

Written for insulin concentration of 100 units of regular insulin per 500ml of NS. Therefore all units/hr must be multiplied by 5 as below to get the correct ml/hr for the pump.

For Initiation, pump subjects start at 1/2 standard algorithm, nocturnal basal subjects start at 1/4 standard, and AM basal insulin subjects start at 1/8 standard.

Below Goal Range Less than 90 mg/dL	Within Goal Range Less than 90 – 120 mg/dL	Above Goal Range Over 120 mg/dL

Less than 70 mg/dL
 
• Turn off infusion• Follow Hypoglycemia orders• Recheck BG and re-retreat every 15. Then proceed according to the appropriate column of this table for next measured BG. 
70 – 80 mg/dL
 
• Turn off infusion.• Check BG in 30 minutes.• Once BG is > 80mg/dl resume insulin infusion after moving one column to the left	
If BG decreased by 30 mg/dL between checks
 
• Move left one algorithm and adjust rate per BG.• If already at 1/2 Standard, move left to 1/4 Standard (Low) Algorithm and adjust rate per BG 
If BG DECREASED by 1-30mg/dl or INCREASED by any amount
 
• Adjust rate in current algorithm per BG	
If BG decreased by more than 50 mg/dL
 
• Move left one algorithm and adjust rate per BG.• If already at 1/2 Standard, move left to 1/4 Standard (Low) Algorithm and adjust rate per BG.• Check BG in 15 minutes if decrease was over 100 mg/dL. 
If BG decreased by 25 – 50 mg/dL
 
• Adjust rate in current algorithm per BG

80-90 mg/dL
 
If BG decreased by 30 mg/dL or more, or previous BG 80-90 mg/dL
 
• Move left one algorithm and adjust rate per BG.• If already at 1/2 Standard move left to 1/4 Standard Algorithm and adjust rate per BG.• If already at 1/4 algorithm, may remain there. 
If BG decreased less than 30 mg/dL and/or previous BG was in goal range
 
• Adjust rate in current algorithm per BG.		
If BG increased by any amount, remained the same or decreased by less than 25 mg/dL
 
Step 1. Remain in current algorithm and adjust rate per BG.
 
Step 2. If after remaining in current algorithm and next BG check continues to increase by any amount or decrease by less than 25 mg/dL, move right one algorithm
 
Step 3. Check BG at the next time-point per protocol, and restart at step 1 if appropriate.

Insulin Infusion Algorithm

BG mg/dL	1/8 Standard units/hr (ml/hr)	1/4 Standard units/hr (ml/hr)	1/2 Standard (Low) units/hr (ml/hr)	Algorithm 1 (Standard) units/hr (ml/hr)	Algorithm 2 units/hr (ml/hr)	Algorithm 3 units/hr (ml/hr)	Algorithm 4 units/hr (ml/hr)	Algorithm 5 units/hr (ml/hr)	Algorithm 6 units/hr (ml/hr)
80-90	0.1 (0.5ml/hr)	0.2 (1ml/hr)	0.3 (1.5ml/hr)	0.5 (2.5ml/hr)	0.6 (3ml/hr)	0.8 (4ml/hr)	1.0 (5ml/hr)	1.2 (6ml/hr)	1.4 (7ml/hr)
90 - 120	0.2 (1ml/hr)	0.3 (1.5ml/hr)	0.5 (2.5ml/hr)	0.7 (3.5ml/hr)	0.8 (4ml/hr)	1.0 (5ml/hr)	1.2 (6ml/hr)	1.4 (7ml/hr)	1.6 (8ml/hr)
121-160	0.3 (1.5ml/hr)	0.4 (2ml/hr)	0.7 (3.5ml/hr)	0.9 (4.5ml/hr)	1.1 (5.5ml/hr)	1.2 (6ml/hr)	1.4 (7ml/hr)	1.6 (8ml/hr)	1.8 (9ml/hr)
161-180	0.4 (2ml/hr)	0.5 (2.5ml/hr)	1 (5ml/hr)	1.1 (5.5ml/hr)	1.3 (6.5ml/hr)	1.5 (7.5ml/hr)	1.7 (8.5ml/hr)	1.9 (9.5ml/hr)	2.1 (10.5ml/hr)
181-220	0.5 (2.5ml/hr)	0.6 (3ml/hr)	1.2 (6ml/hr)	1.3 (6.5ml/hr)	1.5 (7.5ml/hr)	1.7 (8.5ml/hr)	1.9 (9.5ml/hr)	2.1 (10.5ml/hr)	2.3 (11.5ml/hr)
221-260	0.6 (3ml/hr)	0.8 (4ml/hr)	1.5 (7.5ml/hr)	1.7 (8.5ml/hr)	1.9 (9.5ml/hr)	2.1 (10.5ml/hr)	2.3 (11.5ml/hr)	2.5 (12.5ml/hr)	2.7 (13.5ml/hr)
261-300	0.8 (4ml/hr)	1 (5ml/hr)	2 (10ml/hr)	2.2 (11ml/hr)	2.4 (12ml/hr)	2.6 (13ml/hr)	2.8 (14ml/hr)	3.0 (15ml/hr)	3.2 (16ml/hr)
Over 300	1 (5ml/hr)	1.3 (6.5ml/hr)	2.5 (12.5ml/hr)	2.8 (14ml/hr)	3.0 (15ml/hr)	3.2 (16ml/hr)	3.4 (17ml/hr)	3.6 (18ml/hr)	4.0 (20ml/hr)

1. Monitor BG and adjust per algorithm above. Check BG every 30 minutes until it is within goal range of 90-120. BGs may then be checked every hour.
 - a. BG target range: 90-120 mg/dL at all times
 - b. Maintain blood glucose within range.
 - c. If need to go above algorithm 6:

Algorithm 7 = algorithm 6 + algorithm 1
 Algorithm 8 = algorithm 6 + algorithm 2 and so on
 - d. The investigator (PI/SUB-I) may adjust insulin drip at their discretion if adjustments are deemed necessary outside of the algorithms.

*** In the event of hypoglycemia (BG < 70mg/dl)

If BG < 50 mg/dL:

D/C INSULIN DRIP, Give 1 Amp (25 g) D50 IV; recheck BG q 15 minutes
⇒ When BG \geq 100 mg/dL, wait 1 hour, then restart insulin drip at 50% of original rate

If BG 50-69 mg/dL:

D/C INSULIN DRIP If symptomatic (or unable to assess), give 1/2 Amp (12.5 g) D50 IV; recheck BG q 15 minutes
If asymptomatic, give 1/4 Amp (6.25 g) D50 IV OR 8 ounces Juice; recheck BG
⇒ When BG \geq 100 mg/dL, wait 1 hour, then restart drip at 75% of original rate

Appendix D. Quality of Life Questionnaires

WHO-5 Well-Being Index

DIRECTIONS: Please indicate for each of the five statements which is closest to how you have been feeling over the last two weeks. Notice that higher numbers mean better well-being.

Example: If you have felt cheerful and in good spirits more than half of the time during the last two weeks, put a tick in the box with the number 3 in the upper right corner.

Over the last two weeks:	All of the time	Most of the time	More than half of the time	Less than half of the time	Some of the time	At no time
1. I have felt cheerful and in good spirits.	5	4	3	2	1	0
2. I have felt calm and relaxed.	5	4	3	2	1	0
3. I have felt active and vigorous.	5	4	3	2	1	0
4. I woke up feeling fresh and rested.	5	4	3	2	1	0
5. My daily life has been filled with things that interest me.	5	4	3	2	1	0

T1-DDS

Instructions

Living with type 1 diabetes can be tough. Listed below are a variety of distressing things that many people with type 1 diabetes experience. Thinking back over the past month, please indicate the degree to which each of the following may have been a problem for you by circling the appropriate number. For example, if you feel that a particular item was not a problem for you over the past month, you would circle "1". If it was very tough for you over the past month, you might circle "6".

		Not a problem	A slight problem	A moderate problem	A somewhat serious problem	A serious problem	A very serious problem
1	Feeling that I am not as skilled at managing diabetes as I should be.	1	2	3	4	5	6
2	Feeling that I don't eat as carefully as I probably should.	1	2	3	4	5	6
3	Feeling that I don't notice the warning signs of hypoglycemia as well as I used to.	1	2	3	4	5	6
4	Feeling that people treat me differently when they find out I have diabetes.	1	2	3	4	5	6
5	Feeling discouraged when I see high blood glucose numbers that I can't explain.	1	2	3	4	5	6
6	Feeling that my family and friends make a bigger deal out of diabetes than they should.	1	2	3	4	5	6
7	Feeling that I can't tell my diabetes doctor what is really on my mind.	1	2	3	4	5	6
8	Feeling that I am not taking as much insulin as I should.	1	2	3	4	5	6
9	Feeling that there is too much diabetes equipment and stuff I must always have with me.	1	2	3	4	5	6
10	Feeling like I have to hide my diabetes from other people.	1	2	3	4	5	6
11	Feeling that my friends and family worry more about hypoglycemia than I want them to.	1	2	3	4	5	6
12	Feeling that I don't check my blood glucose level as often as I probably should.	1	2	3	4	5	6
13	Feeling worried that I will develop serious long-term complications, no matter how hard I try.	1	2	3	4	5	6

		Not a problem	A slight problem	A moderate problem	A somewhat serious problem	A serious problem	A very serious problem
14	Feeling that I don't get help I really need from my diabetes doctor about managing diabetes.	1	2	3	4	5	6
15	Feeling frightened that I could have a serious hypoglycemic event when I'm asleep.	1	2	3	4	5	6
16	Feeling that thoughts about food and eating control my life.	1	2	3	4	5	6
17	Feeling that my friends or family treat me as if I were more fragile or sicker than I really am.	1	2	3	4	5	6
18	Feeling that my diabetes doctor doesn't really understand what it's like to have diabetes.	1	2	3	4	5	6
19	Feeling concerned that diabetes may make me less attractive to employers.	1	2	3	4	5	6
20	Feeling that my friends or family act like "diabetes police" (bother me too much).	1	2	3	4	5	6
21	Feeling that I've got to be perfect with my diabetes management.	1	2	3	4	5	6
22	Feeling frightened that I could have a serious hypoglycemic event while driving.	1	2	3	4	5	6
23	Feeling that my eating is out of control.	1	2	3	4	5	6
24	Feeling that people will think less of me if they knew I had diabetes.	1	2	3	4	5	6
25	Feeling that no matter how hard I try with my diabetes, it will never be good enough.	1	2	3	4	5	6
26	Feeling that my diabetes doctor doesn't know enough about diabetes and diabetes care.	1	2	3	4	5	6
27	Feeling that I can't ever be safe from the possibility of a serious hypoglycemic event.	1	2	3	4	5	6
28	Feeling that I don't give my diabetes as much attention as I probably should.	1	2	3	4	5	6

3 ABBREVIATIONS

Abbreviations pertain to the SAP only (not the TFLs).

ADaM	analysis data model
ACT	arginine challenge test
AE	adverse event
ANCOVA	analysis of covariance
ATC	anatomical therapeutic chemical
AUC	area under the concentration-time curve
CDISC	Clinical Data Interchange Standards Consortium
CGM	continuous glucose monitoring
CI	confidence interval
CSR	Clinical Study Report
CV	coefficient of variation
EC	Early Clinical
ECG	electrocardiogram
eCRFs	electronic Case Report Forms
GLP-1	glucagon-like peptide 1
HbA1c	hemoglobin A1c
ICH	International Conference on Harmonisation
LS	least squares
MedDRA	Medical Dictionary for Regulatory Activities
MMTT	Mixed Meal Tolerance Test
ms	millisecond
OBV	overnight baseline visit
PD	pharmacodynamics
PK	pharmacokinetic
QOL	Quality of Life
QTc	QT correction; QT interval corrected for heart rate
QTcB	QTc calculated using the Bazett correction
QTcF	QTc calculated using the Fridericia correction
SAP	Statistical Analysis Plan

SC subcutaneous
T1-DDS Type 1 – Diabetes Distress Scale
TEAE treatment-emergent adverse event
TFLs tables, figures, and listings

4 INTRODUCTION

This SAP has been developed after review of the clinical study protocol (Final Version 1.0 dated 03 April 2017 and Protocol Amendment 2 dated 26 October 2019).

This SAP describes the planned analysis of the efficacy, PD, safety, and tolerability data from this study. A detailed description of the planned TFLs to be presented in the Clinical Study Report (CSR) is provided in the accompanying TFL shell document.

The intent of this document is to provide guidance for the statistical analyses of safety, tolerability, efficacy, PK and PD data. In general, the analyses are based on information from the protocol, unless they have been modified by agreement between REMD Biotherapeutics and Covance Early Clinical (EC) Biometrics. A limited amount of information concerning this study (eg, objectives, study design) is given to help the reader's interpretation. This SAP must be finalized prior to the lock of the clinical database for this study. When the SAP and TFL shells are agreed upon and finalized, they will serve as the template for this study's CSR.

This SAP supersedes the statistical considerations identified in the protocol; where considerations are substantially different, they will be so identified. If additional analyses are required to supplement the planned analyses described in this SAP, they may be performed and will be identified in the CSR. Any substantial deviations from this SAP will be agreed upon between REMD Biotherapeutics and Covance EC Biometrics and identified in the CSR.

This SAP is written with consideration of the recommendations outlined in the International Conference on Harmonisation (ICH) E9 guideline entitled, "Guidance for Industry: Statistical Principles for Clinical Trials" and the ICH E3 guideline entitled, "Guidance for Industry: Structure and Content of Clinical Study Reports."^{1,2}

5 STUDY OBJECTIVES

5.1 Primary Objective

- To compare the effects of multiple doses of REMD-477 versus placebo on change from baseline at Week 12 in daily insulin requirements.

5.2 Secondary Objectives

- To compare the effects of multiple doses of REMD-477 versus placebo on measures of glycemic control including change from baseline at Week 13 in fasting glucose and glucose area under the curve (AUC) after mixed meal tolerance test (MMTT) – Part A only.
- To compare the effects of multiple doses of REMD-477 versus placebo on change from baseline at Week 12 in average daily 24-h blood glucose concentration and time within target range as assessed by continuous glucose monitoring (CGM) and seven-point glucose profile.

- To compare the effects of multiple doses of REMD-477 versus placebo on the product of the ratio of average glucose (Week 12/Baseline) and ratio of average insulin use (Week 12/Baseline).
- To evaluate the safety and tolerability of multiple doses of REMD-477 versus placebo.
- To compare the incidence of hypoglycemic episodes after multiple doses of REMD-477 versus placebo.
- To compare the effects of multiple doses of REMD-477 versus placebo on change from baseline at Week 13 in hemoglobin A1c (HbA1c).
- To compare the proportion of subjects who achieve HbA1c reduction of $\geq 0.4\%$ after multiple doses of REMD-477 versus placebo at Week 13.
- To compare the effects of multiple doses of REMD-477 versus placebo on pancreatic beta cell function as measured by change from baseline at Week 13 in C-peptide AUC after a MMTT and arginine challenge test (for a subset of subjects who were enrolled prior to Protocol Amendment #1) – Part A only.
- To compare the effects of multiple doses of REMD-477 versus placebo on pancreatic alpha cell function as measured by change from baseline at Week 13 in peripheral levels of fasting glucagon, active and total glucagon-like peptide 1 (GLP-1), and glucagon and GLP-1 (active and total) AUC after MMTT – Part A only.
- To determine REMD-477 plasma concentrations and formation of anti-REMD-477 antibodies after multiple dosing.

5.3 Exploratory Objectives

- To compare the effects of multiple doses of REMD-477 versus placebo on change from baseline at Week 13 in body weight.
- To compare the effects of multiple doses of REMD477 versus placebo on change from baseline at week 13 in Quality of Life (QOL) score.
- To explore the effects of multiple doses of REMD-477 on the intrahepatic lipid content as measured by magnetic resonance imaging – proton density fat fraction (MRI-PDFF) (for a subset of subjects in Part B only)
- To explore the effects of multiple doses of REMD-477 on the intrahepatic lipid content as measured by FibroScan® (for a subset of subjects in Part B only)

6 STUDY DESIGN

This is a randomized, placebo-controlled, double-blind study to evaluate the efficacy, safety, and PD of multiple doses of REMD-477 in subjects who have Type 1 diabetes and are currently receiving insulin treatment. This study will determine whether glucagon receptor blockade with REMD-477 can decrease daily insulin requirements and improve glycemic control after 12 weeks of treatment in subjects diagnosed with Type 1 diabetes with fasting C-peptide < 0.7 ng/mL at Screening.

The two part study (Parts A and B) will be conducted at multiple sites in the United States. In each part, approximately 75 subjects (150 subjects in total across Parts A and B) with Type 1 diabetes on stable doses of insulin will be randomized in a 1:1:1 fashion into one of three treatment groups (placebo, 35 mg REMD-477, or 70 mg REMD-477). The enrollment of Part B may be initiated prior to the completion of Part A. Subjects will receive once weekly SC injections of investigational product for 12 weeks and be followed for an additional 12 weeks during washout in the Safety Follow-up Period. At baseline, throughout the treatment period, and during the 12-week Safety Follow-up Period, subjects will be evaluated for measures of glycemic control, daily insulin requirements, and safety. For subjects enrolled in Parts A and B, CGM and seven-point glucose profile will be conducted to assess the effect of REMD-477 versus placebo on glucose variability and metabolic control. For a subset of subjects in Part A who were enrolled prior to Protocol Amendment #1, beta cell function after mixed meal and arginine challenge will be examined. For subjects in Part A, alpha cell function will be assessed by measuring fasting glucagon, active and total GLP-1, and glucagon and GLP-1 (active and total) AUC after the MMTT.

For a subset of subjects in Part A who were enrolled prior to Protocol Amendment #1, eligible subjects will be admitted to the clinical research unit (CRU) on the evening of the Overnight Baseline Visit (OBV) (which can occur between Study Day -8 to Day -2), the Week 13 Visit (admission Day 84), and the Week 24 Visit (admission Day 161). For ongoing subjects at the time of the Protocol Amendment #1, the overnight admissions to the CRU at Baseline, Week 13 and Week 24 will not occur.

For a subset of subjects in Part B, the magnetic resonance imaging – proton density fat fraction (MRI-PDFF) and FibroScan® (where feasible) will be performed prior to dosing on Day 1 (or up to 7 days prior to the Day 1 visit, after all other inclusion and exclusion criteria have been met) and on Day 85 (+/- 2 days) of Week 13.

[figure not shown]

Figure 1: Part A Study Design Schema

[figure not shown]

Figure 2: Part B Study Design Schema

7 TREATMENTS

The following is a list of the study treatment abbreviations and ordering that will be used in the TFLs.

Study Treatment Name	Treatment Order on TFLs
35 mg REMD-477 (SC)	1
70 mg REMD-477 (SC)	2
Placebo (SC)	3

8 SAMPLE SIZE JUSTIFICATION

The power calculation for the primary endpoint (difference in the change from baseline in daily insulin use) is based on the assumption that daily insulin requirement will not change in the

placebo group and will decrease in the REMD-477 treatment groups. Based on an expected coefficient of variation of the daily insulin requirement of ~36%, it is estimated that ≥ 22 subjects in each group (treatment and placebo) will be sufficient to detect a difference of at least 30% with a power of 0.8, and an alpha value of 0.05. To ensure statistical power, and to avoid inadequacy due to unanticipated subject dropout, an N=25/group is used for each Part of this study.

9 DEFINITION OF ANALYSIS POPULATIONS

The analysis populations apply to both Parts A and B separately.

The **All Subjects Population** will consist of any subjects who enrolled on to the study (signed informed consent) and had study assessments recorded on the database as per the protocol.

The **Efficacy Population** will consist of all subjects who received at least one dose of REMD-477 and have evaluable average daily insulin use data.

The **PD Population** will consist of all subjects who received at least one dose of study drug (REMD-477 or placebo) and have evaluable PD data.

The **Safety Population** will consist of all subjects who received at least one dose of study drug (REMD-477 or placebo) and have at least one post-dose safety assessment.

The **PK Population** will consist of all subjects who received at least one dose of REMD-477 and have evaluable PK data.

All protocol deviations that occur during the study will be considered prior to database lock for their severity/impact and will be taken into consideration when subjects are assigned to analysis populations. Details of subject assignment to the analysis populations will be summarized and listed.

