10 STATISTICAL METHODOLOGY

10.1 General

Data listings will be provided for the All Subjects Population. Summary statistics and statistical analyses will be performed for subjects included in the relevant analysis populations (Safety/PK/PD).

For continuous data, summary statistics will include the arithmetic mean, arithmetic standard deviation, median, minimum, maximum, and number. For log-normal data (eg, the Mixed Meal Tolerance Test [MMTT] parameters: areas under the concentration-time curve [AUCs]), the geometric mean and geometric coefficient of variation (CV%) will also be presented. For categorical data, frequency counts and percentages will be presented. Data listings will be provided for all subjects. For the calculation of summary statistics and statistical analysis, unrounded data will be used.

Outputs will be created separately for Parts A and B.

Missing values will not be imputed.

Data analysis will be performed using SAS® Version 9.4.

Analysis Data Model (ADaM) datasets will be prepared using Clinical Data Interchange Standards Consortium (CDISC) ADaM Version 2.1, and CDISC ADaM Implementation Guide Version 1.1. Pinnacle 21 Community Validator Version 2.2.0 will be utilized to ensure compliance with CDISC standards.

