10.3 Efficacy and Pharmacodynamic Assessments

10.3.1 Efficacy Primary Endpoint

- Change from baseline at Week 12 in daily insulin use.

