10.3.4.2 Efficacy - Daily Insulin Use

Hypothesis:

Multiple doses of REMD-477 will significantly decrease daily insulin use versus placebo treatment at Week 12.

The daily insulin use will be derived as the average daily insulin over a collection period ranging from either 3 or 7 days. For the Lead-In Period (Part A – 14 to 28 days; Part B – 7 to 14 days), the average daily insulin use will be derived from a period of 14 days. For Days 1, 8, 15, and 22, the average daily insulin use will be derived from the individual insulin values over the next 7 days. For Days 50, 78, 106 and 134, the average daily insulin use will be derived from the individual insulin values over the next 3 days. Baseline assessment is the derived average daily insulin use during the Lead-In (Part A – 14 to 28 days; Part B – 7 to 14 days) period. The measurements will be summarized separately for Parts A and B by treatment group and timepoint along with changes and percentage changes from baseline. Figures of mean average daily insulin use, changes and percentage changes from baseline will be presented separately for Parts A and B by treatment.

The changes from baseline and percentage change from baseline measurements will be statistical analyzed separately for Parts A and B. The statistical analysis for the changes from baseline measurements will be used to test the primary hypothesis, while the statistical analysis for the percentage changes from baseline measurements will be used as a sensitivity analysis. A sequential stepwise hypothesis and a Hochberg testing procedure will be utilized to allow for multiple testing while preserving the overall significance level of the trial.

For Parts A and B separately a repeated measures ANCOVA will be used to compare the changes and percentage changes from baseline in daily insulin use between treatment groups for each timepoint. Dependent variables will be treatment, day, and the treatment by day interaction. The baseline variable will be used as a covariate. Covariates may be added to the above model depending on the results from the comparison of baseline characteristics as detailed in section [10.3.4.1](#)

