Subject will be used as a random effect. The least squares (LS) mean for each treatment will be presented for each timepoint. Also, the difference between treatments, the 95% confidence interval (CI) of the differences, and p-value associated with the null-hypothesis of no difference will be reported for each timepoint where applicable based on the sequential testing methods as described below.

Step 1: The first step of the sequential testing will consist of a test for the effect of REMD-477. The Hochberg procedure will be used to assess the statistical significance of two tests: one for the superiority of 70 mg REMD-477 compared to placebo, the other for the superiority of 35 mg REMD-477 compared placebo. If the larger of the two p-values is less than the significance level (ie, 0.05), then both tests are considered to have reached statistical significance. Otherwise, if the smaller of the two p-values is less than half of the significance level (ie 0.025), then the corresponding test is considered to have reached statistical significance.

Step 2: If at least one of the two doses of REMD-477 is found to be superior to placebo, then the two doses of REMD-477 will be compared using the same significance level as that used to claim significance of either dose of REMD-477.

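### As worded, the SAP's Efficacy Population leaves out every placebo subject, although the primary test is against placebo; probably a drafting slip, but wrong as it stands

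*SAP*

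**What the plan says.** SAP section 9 defines five populations, applied to Parts A and B separately. Of these, the Efficacy set "will consist of all subjects who received at least one dose of REMD-477 and have evaluable average daily insulin use data". By contrast, the PD set is "all subjects who received at least one dose of study drug (REMD-477 or placebo) and have evaluable PD data", and the Safety Population has the same dosing condition as PD. The PK Population is "all subjects who received at least one dose of REMD-477 and have evaluable PK data".

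The primary endpoint is change from baseline in daily insulin use at Week 12, placed under the heading "Efficacy Primary Endpoint" (SAP 10.3.1). The hypothesis in SAP 10.3.4.2 is "Multiple doses of REMD-477 will significantly decrease daily insulin use versus placebo treatment at Week 12". Step 1 makes two comparisons: "one for the superiority of 70 mg REMD-477 compared to placebo, the other for the superiority of 35 mg REMD-477 compared placebo". Step 2, the comparison of the two doses, opens with a condition: "If at least one of the two doses of REMD-477 is found to be superior to placebo".

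On which set serves which analysis, SAP 10.1 says only that summaries and analyses "will be performed for subjects included in the relevant analysis populations (Safety/PK/PD"). Efficacy is not in that list, and 10.3.4.2 names no population.

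**The concern.** Efficacy is the only population defined by insulin-use data, and its name matches the headings over the primary endpoint and its analysis. It is therefore the natural set for the primary test. Yet its dosing condition can be met only in the two active arms.

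If the definition is applied as written, the primary comparison has no comparator. The more realistic cost is that whoever assigns subjects to populations must override the written rule, and whoever programs the primary analysis must infer its set from headings. Both decisions should be settled in the SAP before database lock. Section 9 also requires population assignments to be summarized and listed, and protocol section 10 (Study Disposition and Demographic Data) requires a reason for each exclusion from an analysis set. Under the current wording those outputs would show every placebo subject as excluded from Efficacy.

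**Working it through.** **1. Can the phrase be shorthand for study drug?** The four populations that require a dose compare as follows.

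| Population | Dose required | Placebo subjects can qualify? |
|---|---|---|
| PD | REMD-477 or placebo | Yes |
| Safety | REMD-477 or placebo | Yes |
| PK | REMD-477 | No, and none are needed |
| Efficacy | REMD-477 | No, but they are needed |

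Two of the four name placebo and two do not. SAP section 7 lists placebo as a treatment distinct from 35 mg and 70 mg REMD-477. The section has its own wording for a set that includes placebo, and the Efficacy line does not use it.

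**2. Does anything else repair it?** The protocol's statistical section defines no efficacy population, and SAP section 4 says the SAP supersedes that section. SAP section 12 (changes from the protocol) lists no change of population.

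**3. Does the design rely on a placebo group?** SAP section 8 powers the primary comparison with at least 22 subjects in each group, placebo included, for a 30% difference, CV of about 36%, power 0.8 and alpha 0.05. Sidedness is not stated; two-sided is assumed here.

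- Normal approximation: n = 2 × [0.36 × (1.960 + 0.842) / 0.30]² = 22.6, so 23 per group.
- t-test: 23.6, so 24 per group.

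Both are within 2 of the plan's 22. At the planned 25 per group, power is about 0.84 (normal) or 0.82 (t). These figures presuppose a placebo arm of that size.

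**4. Counts under each wording.** Assume exact 1:1:1 allocation, with all subjects dosed and evaluable.

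- Per arm: 75 / 3 = 25 in each Part.
- As written: 25 + 25 = 50 per Part, with 0 of 25 placebo subjects.
- With placebo included: 25 + 25 + 25 = 75 per Part.

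**5. Comparisons, if the Efficacy set as written serves the primary test.** Each Part has 2 comparisons in Step 1 and 1 in Step 2, making 3.

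- Step 1: no placebo data, so 0 of 2 can be run.
- Step 2: the 70 mg versus 35 mg contrast could be computed, but it requires a Step 1 win over placebo, so 0 of 1 can be reached.
- Total: 0 of 3 per Part, and 0 of 6 over both Parts.

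With placebo included, both Step 1 tests can be run and Step 2 can be reached.

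**6. A separate, minor mismatch in the same analysis.** SAP 10.3.4.2 derives Lead-In insulin use from 14 days without separating the Parts. The protocol collects 7 days in Part B (section 7, Continuous Glucose Monitoring and Glucose Blood Monitoring; Appendix A Part B, footnote h). SAP 10.1 rules out imputation, so if exactly 7 diary days exist, their mean is the same under either window.

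**The case against.** The strongest reply is that the loss of the primary test mixes two ways of reading. No sentence in the SAP assigns the Efficacy Population to the primary test. If 10.1 is read as literally as section 9, the insulin analysis falls to one of the listed sets, most naturally PD. That set includes placebo, and both Step 1 tests can be run. The SAP gives this some support: the product of the glucose and insulin-use ratios sits among its pharmacodynamic endpoints (10.3.2). This point stands to the extent that the zero-of-three count is conditional. It does not rescue the text, because the set named for efficacy would then serve no stated analysis, and the PD set asks for evaluable PD data rather than evaluable insulin-use data.

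A second reply is that the slip cannot bias a result unnoticed: a placebo comparison without placebo subjects fails at once, and population assignment is reviewed before database lock. That is fair, and it limits the severity. A third is that the TFL shells, which accompany the SAP, may name the population for each table. They were not available, so the gap is shown for the SAP text only.

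On the Part B window, the SAP does acknowledge a Lead-In of 7 to 14 days. Because that period can run to 2 weeks, the two windows could give different means if a subject's diary extends beyond 7 days.

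**Conclusion.** The concern holds. The Efficacy Population is wrong as written, and the set for the primary analysis is implied rather than stated. The intent to include placebo is clear from the treatment list, power statement, hypothesis and Step 1 tests, so this is most likely a drafting slip and the primary test is not expected to be lost.

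Taken at its word, and if used for the primary test, the definition keeps at most 50 of 75 subjects per Part, none on placebo, and blocks all three planned comparisons in each Part. Those counts assume 25 per arm, all dosed and evaluable. The error affects specification only; it does not alter sample size, power or alpha. It should be fixed because the rule is operative and concerns the primary endpoint. The Part B window is a wording mismatch with little or no numerical effect if the available days are averaged.

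**What to change.** - **SAP section 9:** give the Efficacy Population the dosing condition already used for PD and Safety (study drug, meaning REMD-477 or placebo), and keep its insulin-use data condition.
- **SAP 10.1:** add Efficacy to the list of analysis populations.
- **SAP 10.3.4.2:** state that the primary analysis uses the Efficacy Population.
- **SAP 10.3.4.2, separately:** give the Lead-In insulin window as 14 days for Part A and 7 days for Part B, to match the protocol's data collection.

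The cost is one phrase, one word and two short edits, with no change to the design. The TFL shells should be checked for the same wording.
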